5.2.1.3.4. Initial tumour assessment

Not applicable.

5.2.1.4. Extent of exposure and treatment compliance

Treatment duration for trifluridine/tipiracil

Treatment duration (months) for trifluridine/tipiracil is defined as $[(\min(\text{first intake date of the last cycle} + 27 \text{ days, death date}) - \text{first trifluridine/tipiracil intake date}) + 1] / 30.44$.

Treatment duration for futuximab/modotuximab

Treatment duration (months) for futuximab/modotuximab is defined as $[(\min(\text{first infusion date of the last cycle} + 27 \text{ days, death date}) - \text{first futuximab/modotuximab infusion date}) + 1] / 30.44$.

For trifluridine/tipiracil and futuximab/modotuximab, in case of missing or incomplete first intake date of the last cycle, the last intake date of the last cycle will be considered.

Cycle duration for trifluridine/tipiracil

Duration of cycle i (weeks) for trifluridine/tipiracil is defined as $[(\text{first trifluridine/tipiracil intake of cycle } (i+1)) - (\text{first trifluridine/tipiracil intake of cycle } i)] / 7$.

Of note, the duration of the last cycle for trifluridine/tipiracil will be estimated to be 28 days for the calculation of Dose Intensity and Relative Dose Intensity at the last cycle.

Cycle duration for futuximab/modotuximab

Duration of cycle i (weeks) for futuximab/modotuximab is defined as $[(\text{first futuximab/modotuximab infusion of cycle } (i+1)) - (\text{first futuximab/modotuximab infusion of cycle } i)] / 7$.

Of note, the duration of the last cycle for futuximab/modotuximab will be estimated to be 28 days for the calculation of Dose Intensity and Relative Dose Intensity at the last cycle.

Follow-up duration

The follow-up duration (months) is calculated as the duration between the last available date and the inclusion date $[\text{last available date}^* - \text{inclusion date} + 1] / 30.44$. The events of interest are being alive or lost to follow-up and death is censored.

^{*}Last available date is defined as date of death if patient died, and as maximum date among completed dates relative to patient's information otherwise.

Number of cycles for trifluridine/tipiracil

The number of cycles with trifluridine/tipiracil will be defined based on trifluridine/tipiracil administration page. A patient is considered to enter in a cycle if there is at least one answer 'Yes' to the question 'Has the patient taken his/her morning (or evening) intake?'.

Real administrated dose (mg) for trifluridine/tipiracil

On a time period, real administered dose for trifluridine/tipiracil (mg) = Number of capsules 15 mg taken*15 + Number of capsules 20 mg taken*20

With:

- Number of capsules taken = Number of capsules dispensed - Number of capsules returned

Else, if Number of capsules returned is missing, Number of capsules taken = Estimated number of capsules taken.

Number of cycles for futuximab/modotuximab

The number of cycles with futuximab/modotuximab will be defined based on futuximab/modotuximab administration page. A patient is considered to enter in a cycle if the answer is "Yes" to the question "Did the patient receive the IMP infusion?".

Real administrated dose (mg) for futuximab/modotuximab

On a time period, real administered dose for futuximab/modotuximab (mg) = sum of total dose administrated (full + incomplete doses).

In case of incomplete dose administered, the real dose administered can be computed as: planned dose to be given (mg) * actual volume administered (mL) / infusion volume planned (mL)

Planned dose intensity (PDI) for trifluridine/tipiracil (mg/m²/week)

	10 days of intake per cycle
35 mg/m ² (bid) (70 mg/m ² /day)	$70(\text{mg/m}^2/\text{day}) * 10$ 4 (wk)

Planned dose intensity (PDI) for futuximab/modotuximab (mg/kg/week)

	4 weeks of infusion per cycle
9 mg/kg (the first week) then 6 mg/kg (weekly) for cycle 1	$9(\text{mg/kg/week}) + 6(\text{mg/kg/week}) * 3$ 4 (wk)
6 mg/kg (weekly) for next cycles	$6(\text{mg/kg/week}) * 4$ 4 (wk)

Cumulative dose

The cumulative dose (mg/m²) for trifluridine/tipiracil per patient in a time period (during the treatment period or per cycle) is the sum of the total dose that the patient received within that period according to the compliance.

$$\text{Cumulative dose (mg/m}^2\text{)} = \sum_{\text{timeperiod}} \left(\frac{\text{Real Administrated dose (mg)}}{\text{BSA (m}^2\text{)}} \right)$$

Where BSA is calculated in the ClinTrial database by the data management.

The cumulative dose (mg/kg) for the futuximab/modotuximab per patient in a time period (during the treatment period or per cycle) is the sum of the total dose that the patient received within that period according to the compliance.

$$\text{Cumulative dose (mg/kg)} = \sum_{\text{timeperiod}} \left(\frac{\text{Real Administrated dose (mg)}}{\text{weight (kg)}} \right)$$

Dose intensity (DI) per patient

The dose intensity (mg/m²/week) for trifluridine/tipiracil per patient is defined as the cumulative dose (mg/m²) received during the treatment period divided by the total treatment duration in weeks.

$$DI (\text{mg/m}^2/\text{wk}) \text{ per patient} = \frac{\text{Cumulative dose (mg/m}^2\text{)}}{\text{Treatment duration (weeks)}}$$

The dose intensity (mg/kg/week) for the futuximab/modotuximab per patient is defined as the cumulative dose (mg/kg) received during the treatment period divided by the total treatment duration in weeks.

$$DI \text{ (mg/kg/wk) per patient} = \frac{\text{Cumulative dose (mg/kg)}}{\text{Treatment duration (weeks)}}$$

Dose intensity (DI) per cycle

The dose intensity (mg/m²/week) for trifluridine/tipiracil per cycle is defined as the cumulative dose (mg/m²) received during the cycle divided by the cycle duration in weeks.

$$DI \text{ (mg/m}^2\text{/wk) at cycle } i = \frac{\text{Cumulative dose (mg/m}^2\text{) received at cycle } i}{\text{Duration of cycle } i \text{ (weeks)}}$$

The dose intensity (mg/kg/week) for the futuximab/modotuximab per cycle is defined as the cumulative dose (mg/kg) received during the cycle divided by the cycle duration in weeks.

$$DI \text{ (mg/kg/wk) at cycle } i = \frac{\text{Cumulative dose (mg/kg) received at cycle } i}{\text{Duration of cycle } i \text{ (weeks)}}$$

RDI per patient

The RDI (%) per patient is defined as the ratio of the DI to the initial PDI.

$$RDI \text{ (%) per patient} = \frac{DI}{\text{Planned dose intensity}} * 100$$

RDI per cycle

The relative dose intensity (%) per cycle is defined as the ratio of the dose intensity at cycle i to the planned dose intensity.

$$RDI \text{ (%) at cycle } i = \frac{DI \text{ at cycle } i}{\text{Planned dose intensity}} * 100$$

Dose reduction for trifluridine/tipiracil

A cycle with a dose reduction is defined according to the trifluridine/tipiracil dispensing e-CRF page (dose modified since the last cycle (Yes, No)).

Partial dose administered for futuximab/modotuximab

Partial dose administered for the futuximab/modotuximab is defined by an answer “No” at the eCRF interrogation “Was full dose administered?”.

Dispensation postponed for trifluridine/tipiracil

A cycle with a dispensation postponed is defined according to the trifluridine/tipiracil dispensing e-CRF page (Dispensation postponed (Yes, No)).

Unplanned treatment interruption for trifluridine/tipiracil

A treatment interruption is defined according to the number of days between two consecutive dates where the answer is ‘Yes’ to the questions ‘Has the patient taken his/her morning intake’ or ‘Has the patient taken his/her evening intake’ when this duration is one day or longer considering trifluridine/tipiracil administration schedule (5 days on/2 days off, over 14 days followed by a 14-day rest).

Treatment interruption (days) = (date with an answer ‘Yes’ to the questions ‘Has the patient taken his/her morning intake’ or ‘Has the patient taken his/her evening intake’ – following date with an answer ‘Yes’ to the questions ‘Has the patient taken his/her morning intake’ or ‘Has the patient taken his/her evening intake’) -1

Note: only intra-cycle interruptions will be considered

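### Per-patient dose intensity is divided by a duration cut at death, while per-cycle dose intensity uses a fixed 28-day last cycle; this inflates RDI for participants who die on treatment, mainly in cycle 1

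*SAP*

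**What the plan says.** SAP 5.2.1.4 gives two lengths for a participant's last cycle.

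- **Per patient.** Treatment duration for each drug runs from its first dose to the earlier of two dates: the first dose of the last cycle plus 27 days, or death. Dose intensity (DI) is the cumulative dose "received during the treatment period divided by the total treatment duration in weeks". Relative dose intensity (RDI) divides DI by the initial planned dose intensity (PDI).
- **Per cycle.** "the duration of the last cycle for trifluridine/tipiracil will be estimated to be 28 days for the calculation of Dose Intensity", and likewise "the duration of the last cycle for futuximab/modotuximab will be estimated to be 28 days for the calculation of Dose Intensity". The same sentences extend this to RDI at the last cycle. Death is not mentioned.

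PDI is averaged over a 4-week cycle for both drugs. SAP 3.3.1.1 and 3.3.1.2 report RDI in per-patient summaries and in listings by patient and by cycle.

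On missing dates, SAP 5.2.1.4 adds that "in case of missing or incomplete first intake date of the last cycle, the last intake date of the last cycle will be considered".

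**The concern.** DI and PDI must rest on the same time base for their ratio to mean anything. PDI spreads a front-loaded schedule over 28 days: trifluridine/tipiracil is taken only on Days 1-5 and 8-12 (Protocol 6.1.3.2), and futuximab/modotuximab has a larger first dose (Protocol 6.1.1.1). If the DI denominator stops at death, the doses stay in the numerator while the remaining planned days leave the denominator. A participant who stops early for any other reason keeps the full 28 days.

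Participants with identical dosing can therefore get different per-patient RDIs, the higher one going to whoever died. One participant can also have two conflicting RDIs in the listings. No rule in the SAP caps RDI, treats deaths separately or reconciles the two denominators.

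**Working it through.** The SAP states no RDI value to reproduce, so its formulas are applied directly.

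**Inputs**
- Trifluridine/tipiracil PDI (SAP 5.2.1.4): 70 × 10 / 4 = 175 mg/m²/week.
- Futuximab/modotuximab PDI, cycle 1 (SAP 5.2.1.4): (9 + 6 × 3) / 4 = 6.75 mg/kg/week, read as the initial PDI.
- Infusions on Days 1, 8, 15 and 22 (Protocol 6.1.1.3).
- About 25 participants (SAP 1.3).

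**Formulas**, for k complete 28-day cycles and death on day d of the next cycle:
- Per patient, as written: RDI = cumulative dose / ((28k + d)/7) / PDI.
- Per cycle: RDI = last-cycle dose / 4 / PDI.
- Inflation of per-patient RDI relative to a 28-day last cycle: 28(k + 1) / (28k + d). This factor does not depend on how much drug was taken.

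Check: with k = 0 and d = 28, both rules give 100% for each drug.

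**Trifluridine/tipiracil, full dosing until death**

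| Death | Per patient, as written | Per cycle |
|---|---|---|
| Cycle 1, Day 5 | 350/(5/7)/175 = 280% | 350/4/175 = 50% |
| Cycle 1, Day 7 | 350/1/175 = 200% | 50% |
| Cycle 1, Day 12 | 700/(12/7)/175 = 233% | 700/4/175 = 100% |
| Cycle 1, Day 14 | 700/2/175 = 200% | 100% |
| Cycle 1, Day 21 | 700/3/175 = 133% | 100% |
| Cycle 2, Day 12 | 1400/(40/7)/175 = 140% | 100% |
| Cycle 3, Day 12 | 2100/(68/7)/175 = 124% | 100% |
| Cycle 6, Day 12 | 4200/(152/7)/175 = 111% | 100% |
| Cycle 7, Day 12 | 4900/(180/7)/175 = 109% | 100% |

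In cycle 1 the per-patient figure stays between 200% and 280% up to Day 14. From cycle 2 on, Day 12 gives the maximum. A participant who takes all of cycle 1 and stops alive gets 700/4/175 = 100%.

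**Futuximab/modotuximab, full dosing until death**

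| Death | Per patient, as written | Per cycle |
|---|---|---|
| Cycle 1, Day 1 | 9/(1/7)/6.75 = 933% | 9/4/6.75 = 33% |
| Cycle 1, Day 8 | 15/(8/7)/6.75 = 194% | 15/4/6.75 = 56% |
| Cycle 1, Day 22 | 27/(22/7)/6.75 = 127% | 27/4/6.75 = 100% |
| Cycle 2, Day 1 (cycle-2 maximum) | 33/(29/7)/6.75 = 118% | 6/4/6 = 25% |

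The maximum is 104% in cycle 3 and below 100% from cycle 4.

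**Effect on the summary.** Suppose 24 participants have 100% and one has 200% instead of 100%. The mean rises by 100/25 = 4 points, to 104%. The SD goes from 0 to √[(24 × 4² + 96²)/24] = 20 points. The maximum becomes 200% and the median stays at 100%.

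**Missing-date sentence.** Take three fully dosed trifluridine/tipiracil cycles with only the cycle-3 first dose date missing. If 27 days are still added to the last intake (Day 12), the cycle runs to Day 39: 2100/((56 + 39)/7)/175 = 88%. If the last intake simply ends treatment: 2100/((56 + 12)/7)/175 = 124%. The correct value is 2100/12/175 = 100%.

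**The case against.** **Ending exposure at death is a recognised convention.** SAP Table (5.1.2) 2 also brings the date of death into the end of the last cycle. The 28-day rule has its own artefact: a participant who took every scheduled dose until death on Day 5 scores 50%. That is fair, and which rule is better can be debated. But the SAP already uses 28 days for the per-cycle figure and for PDI, so the present mixture is neither convention.

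**The outputs would expose an odd value.** SAP 3.1 requires medians, quartiles and extremes, SAP 3.3.1 gives individual listings, and SAP 3.5.2 lists deaths. This stands as mitigation. It does not tell the reader which of two conflicting RDIs to believe.

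**Such deaths should be few.** Entry requires a life expectancy of at least 12 weeks and ECOG 0-1 (Protocol 5.1.2). As a rough assumption, exponential survival with the protocol's design medians of 8.5 and 12 months gives a 14-day death probability of 1 − exp(−ln 2 × (14/30.44)/median) = 3.7% and 2.6%. That is 0.9 and 0.7 of 25. The entry criteria make a constant hazard from Day 1 too pessimistic. Over any 28 days the same model gives 7.2% and 5.2%, or 1-2 of 25, but that count cannot be paired with a 200% value, because most of those deaths could fall in later cycles.

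**Importance.** A reader might infer that RDI decides whether the combination is deliverable. The documents do not support that. RDI is not an endpoint in Protocol Table (3.4) 1. Tolerability rests on DLT counts and DMC review of all safety data (Protocol 4.1.3.4). DLT evaluability uses administered over planned milligrams (Protocol 4.1.3.2), which this formula does not touch. The randomised part was cancelled for strategic reasons (SAP 1).

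**Conclusion.** The inconsistency is real and should be corrected, as a modest point about a descriptive exposure output. The two denominators in SAP 5.2.1.4 disagree for anyone who dies before Day 28 of the last cycle, and the per-patient figure is always inflated relative to a 28-day last cycle.

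A reader might infer that any death in the last cycle gives an RDI of 200-300%. It does not. For trifluridine/tipiracil that size needs death by Day 14 of cycle 1, and the inflation shrinks quickly as cycles accumulate. Futuximab/modotuximab reaches higher values only in the first days of cycle 1.

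A reader might also take the missing-date sentence as a definite second error with a fixed size. It is only ambiguous: it does not say whether 27 days are added to the substituted date. In a one-cycle participant the overall start date would be missing too, so no clean one-cycle example exists. Missing dates should also be uncommon, since exact administration times go into the e-CRF and intakes into a diary (Protocol 6.2 and 6.4).

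The percentages assume full dosing up to and including the day of death, unchanged weight and body surface area, 28-day earlier cycles, and 6.75 mg/kg/week as the initial futuximab/modotuximab PDI. With reduced dosing the levels fall, but the inflation factor is unchanged.

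**What to change.** In SAP 5.2.1.4, define the denominator of per-patient DI and RDI as the time from first dose to the first dose of the last cycle plus 27 days, without the cut at death. This is the same 28-day last cycle as the per-cycle rule. Keep the death-truncated duration only for the descriptive treatment duration. A cycle-1 death then gives the same RDI per patient and per cycle: for trifluridine/tipiracil, 50% on Day 5 and 100% on Day 14.

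Reword the missing-date sentence so that a missing first dose date of the last cycle is replaced by the visit or planned Day 1 of that cycle. Do not extend the Table (5.1.5) 1 substitution to cycles after the first, because it can place a later cycle at the inclusion date.

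The cost is two sentences and a small programming change. RDI becomes less favourable for participants who die on treatment, which should be stated. If exposure tables already exist, re-run them or footnote the affected participants.

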Title of study: A randomised, open-label, multi-centre, two-arm Phase 3 study comparing futuximab/modotuximab in combination with trifluridine/tipiracil to trifluridine/tipiracil single agent with a Safety Lead-In part in participants with KRAS/NRAS and BRAF wild type metastatic colorectal cancer previously treated with standard treatment and anti-EGFR therapy (COLSTAR) Study Brief Title: Phase 3 study of futuximab/modotuximab in combination with trifluridine/tipiracil versus trifluridine/tipiracil single agent in participants with previously treated metastatic colorectal cancer. Study Public Title: A study of futuximab/modotuximab in combination with trifluridine/tipiracil in participants with previously treated colorectal cancer that has spread (metastatic). Protocol No.: CL3-95026-001 Study name: COLSTAR	
International Coordinator and Steering Committee Chairman: [name] National coordinators and investigators: listed in a separate document	
Study centre(s): Safety Lead-In part Total number of centres: approximately 25 centres. Total number of countries: approximately 8 countries. Randomised part Total number of centres: approximately 200 centres. Total number of countries: approximately 20 countries.	
Study period: 
 - Study duration for the participant: approximately 6.5 months of treatment + follow-up period for survival. - Study initiation date (planned date of first visit first participant (FVFP)): 
 • Safety Lead-In part: Q2 2022. • Randomised part: Q3 2023. - Study completion date (planned date of last visit last participant (LVLP)): 
 Approximately Q4 2026. 	Study development phase: Phase 3 with Safety Lead-In part

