1. INTRODUCTION

This Statistical Analysis Plan (SAP) details the planned analyses to be performed for the Safety Lead-In part, in accordance with the main characteristics of the amended clinical study protocol of 16th August 2022.

The randomised part has been cancelled due to study discontinuation during the Safety Lead-in part for strategic reasons. All information concerning the randomised part is described in the protocol.

The templates for Tables, Listings and Graphs (TLG) are described in a separate document.

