3.3. Treatments

3.3.1. Extent of exposure and treatment compliance

3.3.1.1. Trifluridine/tipiracil

Extent of exposure and treatment compliance of trifluridine/tipiracil will be described in the SS by patient overall including:

- Treatment duration (months).
- Follow-up duration (months) with median based on reverse Kaplan Meier method.
- Number of cycles per patient.
- Cumulative dose (mg/m^2).
- Dose intensity (DI) ($\text{mg}/\text{m}^2/\text{week}$).
- Relative Dose Intensity (RDI) (%).
- Patients with at least one dose reduction (Yes, No).
- Number of dose reductions per patient.
- Number of patients by actual dose level on day 1 of each cycle.
- Patients with at least one dispensation postponed (Yes, No).
- Number of dispensations postponed per patient.
- Patients with at least one unplanned treatment interruption (Yes, No).
- Number of unplanned treatment interruptions per patient.

Individual listings by cycle will be provided including: cumulative dose, planned dose intensity, DI, RDI, total number of tablets given, estimated and returned (15 or 20 mg for trifluridine/tipiracil), cycle duration (weeks), duration of unplanned treatment interruption (days), reason for interruption, dispensation postponed (Yes, No), reason for dispensation postponed (medical reason, non-medical reason) and dose reduction (Yes, No).

Individual listing per patient will be provided including: number of cycles, cumulative dose, planned dose intensity, DI, RDI, treatment duration, unplanned treatment interruption (days), number of dispensations postponed and number of dose reductions.

3.3.1.2. **Futuximab/modotuximab**

Number of infusions per patient, patients with full dose administered, patients with at least one missed infusion, number of cycles with at least one missed infusion, patients with infusion interrupted, patients with infusion rate decreased, cumulative dose (mg/kg), DI (mg/kg/week) and RDI (%) will be described by patient in the SS.

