Individual listing by cycle will be provided including: number of infusions, reason for missed infusion (medical reason, non-medical reason), cumulative dose, planned dose intensity, DI, RDI, cycle duration (weeks), full dose administered (Yes, No), reason for incomplete volume infusion (medical reason, non-medical reason), infusion postponed (Yes, No), reason for postponed infusion (medical reason, non-medical reason), reason for infusion interrupted (medical reason, non-medical reason) and infusion rate decreased (Yes, No).

Individual listing per patient will be provided including: number of cycles, number of infusions, cumulative dose, planned dose intensity, DI, RDI, treatment duration (months), number of cycles with at least one partial dose administered, number of cycles with infusion postponed, number of cycles with infusion interrupted and number of cycles with infusion rate decreased.

3.3.2. **Concomitant treatments and new anti-cancer therapies**

Drug treatments will be described by pharmacological class, pharmacological sub-class, therapeutic class and preferred name (WHO-DD classification, latest available version at the analysis date). All concomitant treatments and new anti-cancer therapies will be summarized according to the following variables:

- Concomitant treatment (Yes, No).
- Received new drug treatment (Yes, No).

Concomitant treatments taken at inclusion, those taken before, during and after the treatment period, as well as new anticancer therapies will be described in the SS.

For concomitant treatments as well as new drug treatments, individual listing will be provided including pharmacological class, pharmacological sub-class, therapeutic class and preferred name, medications start and end date, administration schedule and dose unit administered. The listing will include medications starting on or after the start of study treatment or medications starting prior to the start of study treatment and continuing after the start of study treatment.

3.4. **Efficacy analysis**

The proportion of participants with BOR according to RECIST version 1.1 criteria and using investigator's tumour assessment will be summarized descriptively.

A waterfall plot displaying the best relative change of the sum of the lesions diameters from baseline will be performed.

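### Per-patient relative dose intensity for futuximab/modotuximab is divided by one initial planned value although the SAP lists two; read literally, a fully dosed patient scores 92.6% after three cycles

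*SAP*

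**What the plan says.** SAP 5.2.1.4 gives the planned dose intensity of futuximab/modotuximab in two rows. One is for "9 mg/kg (the first week) then 6 mg/kg (weekly) for cycle 1", divided by four weeks; the other is for "6 mg/kg (weekly) for next cycles", also divided by four weeks. Trifluridine/tipiracil has one row only.

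The section then defines DI per patient as the cumulative dose over the whole treatment period divided by treatment duration in weeks, and RDI per patient as follows: "The RDI (%) per patient is defined as the ratio of the DI to the initial PDI". The formula displayed under that sentence names the denominator simply as the planned dose intensity. RDI per cycle is defined separately, as that cycle's DI over the planned value.

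The results go to two places in SAP 3.3.1.2. In the summary, "cumulative dose (mg/kg), DI (mg/kg/week) and RDI (%) will be described by patient in the SS"; PDI is not in that list, but missed infusions are. The listing does show PDI: "Individual listing per patient will be provided including: number of cycles, number of infusions, cumulative dose, planned dose intensity, DI, RDI".

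The same part of 5.2.1.4 also displays a formula for unplanned trifluridine/tipiracil interruptions: an intake date minus the following intake date, minus 1. The sentence above it says that the dosing schedule is to be taken into account.

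**The concern.** A relative dose intensity should be 100% for a patient who receives every planned dose on time. With one planned value, as for trifluridine/tipiracil, the wording achieves this. With a loading dose in cycle 1 the planned rate changes after the first cycle, and one initial value cannot represent the plan for the whole treatment period.

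On the literal reading the apparent shortfall grows with the number of cycles, so patients treated longest look least compliant. The overall figure also falls below every one of its per-cycle parts. A programmer has to choose a value, and the two listed values give results that differ by about 11 to 12 percentage points for the same patient at 2 to 7 cycles.

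**Working it through.** **Inputs.** All are from SAP 5.2.1.4 unless stated.

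- Cycle 1 PDI: (9 + 6 × 3)/4 = 6.75 mg/kg/week.
- Later-cycle PDI: (6 × 4)/4 = 6.00 mg/kg/week.
- Four weekly infusions per 28-day cycle (Protocol 6.1.1.3).
- Duration: "Treatment duration (months) for futuximab/modotuximab is defined as" the span from the first infusion to 27 days after the first infusion of the last cycle, inclusive, or to death if earlier. An on-time patient with n cycles therefore has 28n days, or 4n weeks.

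The SAP prints no numerical PDI or RDI, so there is no stated figure to reproduce.

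**Fully dosed, on-time patient, constant weight, no reductions.**

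- Cumulative dose = 27 + 24(n − 1) mg/kg.
- DI = [27 + 24(n − 1)]/(4n).
- Cycle-weighted PDI = (6.75 + 6.00(n − 1))/n.

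| Cycles n | Dose (mg/kg) | Weeks | DI | RDI vs 6.75 | RDI vs 6.00 | RDI vs cycle-weighted PDI |
|---|---|---|---|---|---|---|
| 1 | 27 | 4 | 6.750 | 100.0% | 112.5% | 100% |
| 2 | 51 | 8 | 6.375 | 94.4% | 106.3% | 100% |
| 3 | 75 | 12 | 6.250 | 92.6% | 104.2% | 100% |
| 7 | 171 | 28 | 6.107 | 90.5% | 101.8% | 100% |

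The per-cycle RDI of the same patient is (27/4)/6.75 = 100% in cycle 1 and (24/4)/6.00 = 100% in every later cycle.

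**Choice of n.** The documents do not report exposure in the Safety Lead-In part, so the cycle counts are assumptions.

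- Three cycles corresponds roughly to the 2.7-month median PFS of the 9/6 mg/kg arm in the earlier phase 2 study (Protocol 2.2.2): 2.7 × 30.44/28 = 2.9.
- Seven cycles corresponds to the synopsis figure of "approximately 6.5 months of treatment + follow-up period for survival": 6.5 × 30.44/28 = 7.1.

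**Trifluridine/tipiracil check.** Its single PDI is 70 × 10/4 = 175 mg/m²/week. Full dosing gives 700n/(4n) = 175, so RDI is 100% at any n.

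**Death in the last cycle.** Suppose a fully dosed patient dies on day 7 of cycle 2. Dose is 27 + 6 = 33 mg/kg over 35 days, or 5 weeks, so DI = 6.60.

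- Against the two-cycle average of 6.375, per-patient RDI is 103.5%.
- Against the dose scheduled up to death, (27 + 6)/5 = 6.60, it is 100%.
- For per-cycle DI and RDI, however, the SAP fixes the last cycle at 28 days, so cycle 2 scores (6/4)/6.00 = 25%.

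The per-patient and per-cycle duration rules therefore differ, whichever PDI is used.

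**Interruption formula (trifluridine/tipiracil).**

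| Consecutive intakes | As displayed | With order reversed and scheduled days off removed |
|---|---|---|
| Day 2, day 3 | (2 − 3) − 1 = −2 | (3 − 2 − 1) − 0 = 0 |
| Day 2, day 4 | (2 − 4) − 1 = −3 | (4 − 2 − 1) − 0 = 1 |
| Day 5, day 8 (planned gap) | (5 − 8) − 1 = −4 | (8 − 5 − 1) − 2 = 0 |

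**The case against.** The strongest reply is that this is an ambiguity of wording. The PDI table is already laid out by cycle, and *initial* can reasonably mean the plan before any dose reduction. Combined across cycles, that reading gives 100%. This stands as a possible intention. But the SAP does not say it, and does not say how the two rows are to be combined. The table and listing templates are in a separate document that might settle the point; it is not part of what was reviewed.

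A reader might infer that every available reading of the definition fails. That goes too far, because the cycle-weighted reading works and is compatible with the text. A one-cycle patient also scores exactly 100% on the literal reading.

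A reader might also infer that full dosing would be mistaken for a missed infusion, because 92.6% at three cycles is close to the 92.0% that one missed 6 mg/kg infusion gives (69/75). That comparison mixes denominators. Against 6.75 throughout, one missed infusion gives (69/12)/6.75 = 85.2%, well apart from 92.6%. The summary in SAP 3.3.1.2 also reports patients and cycles with missed infusions, and the per-patient listing shows the PDI used.

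Finally, Protocol 8.11.2.2 allows a repeat loading dose, which might seem to push a cycle-weighted RDI above plan. It does not at patient level: re-loading follows two omitted doses, so 12 mg/kg is lost and 3 mg/kg is gained.

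On the interruption formula, the sentence before it makes the intention clear enough that a programmer could recover it. The displayed line is still wrong as a specification.

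**Conclusion.** The point holds as a defect in a definition, with limited consequences. Read literally, the SAP understates per-patient futuximab/modotuximab RDI for a fully dosed, on-time patient by 5.6 points at 2 cycles, 7.4 at 3 and 9.5 at 7. Using 6.00 instead overstates it by 6.3, 4.2 and 1.8 points. These figures assume constant weight, 28-day cycles and no reductions, delays or re-loading; the cycle counts are illustrative.

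The effect is confined to descriptive exposure outputs in one arm: "The randomised part has been cancelled due to study discontinuation during the Safety Lead-in part for strategic reasons". The documents do not support a wider reading in which the tolerability conclusions are compromised. No hypothesis test uses RDI. The dose-intensity rule for DLT evaluability in Protocol 4.1.3.2 compares administered with planned milligrams over the first cycle, so it does not depend on this definition. Cumulative dose and DI are also unaffected. The interruption formula is a separate error of specification for the other drug.

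**What to change.** Define the per-patient futuximab/modotuximab PDI as the cycle-specific values weighted by four planned weeks for each cycle started, (6.75 + 6.00(n − 1))/n mg/kg/week, and set RDI = DI/PDI. For death in the last cycle, state one convention for planned dose and duration, and note that the per-patient duration is cut at death whereas the per-cycle rule fixes the last cycle at 28 days.

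Separately, replace the trifluridine/tipiracil interruption formula with (following intake date − intake date − 1) minus the scheduled days off between the two dates.

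The cost is a few lines of SAP text and the matching programming; no new data are needed. The documentation page in front of the SAP (16.1.9) describes the analyses as already performed. If the outputs are final, check which PDI was programmed, then footnote it in the RDI summary or rerun that table. Check in the same way how interruption days were computed.
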